The American Diabetes Association recommends implementing the Diabetes Prevention Program (DPP) in subjects with prediabetes¹³. This program aims weight reduction increasing physical activity and healthy eating. In controlled settings, DPP has consistently proved to reduce T2D incidence by 58%, with long term benefits¹³. However, to translate this effectiveness to primary care settings is a major challenge. In Latin America, two studies on T2D prevention were done at the same time, funded by an International Diabetes Federation (IDF) initiative¹⁴, with contradictory results. In Venezuela, Florez et al.¹⁵ implemented a Randomized Controlled Trial (RCT) using the US-DPP version, with a multidisciplinary team, on 140 adults with prediabetes and overweight, to receive standard care vs. lifestyle intervention (LSI), during two-years. LSI group lost more than 10% of basal weight compared with 2.3% in the standard care group ($p < 0.001$), none developed T2D compared with 6% of the crude cumulative incidence of T2D in the standard care group ($p < 0.05$)¹⁵, and lipid profile and cardiovascular health score also improved¹⁵. Contrarily, in Colombia, Barengo et al¹⁶ implemented the Finnish Diabetes Prevention Study (DPS) in primary health care centers, provided by specialist in physical activity and nutritionist, on 772 adults with prediabetes, randomly assigned to LSI vs. standard care, during two-years, with no effect on metabolic components, reversion to normoglycemia and T2D incidence were similar between groups¹⁶. A meta-analysis of 36 pragmatic clinical trials of diabetes prevention programs in primary care settings showed a reduction in T2D incidence by 26%¹⁷, less than half than the original studies (58%)^{18,19}. In these studies LSI only showed a pooled mean weight loss 1.57 kg higher than standard care¹⁷, demonstrating the large difficulties to reduce weight of participants at community levels.

This team is leading in Venezuela a transculturalization process incorporating multiple validated components to significantly improve the effectiveness of preventive medicine initiatives for T2D in Venezuela, and by extension, positively impact T2D incidence, prevalence, quality of life, and health care costs²⁰⁻²² (Figure 1).

[figure not shown]

Figure 1: Transculturalization process implemented in Venezuela. From the transcultural adaptation to the evaluation of the effectiveness of evidence-based recommendations. This project represents the step 4.

This process is based on the transcultural Diabetes Nutrition Algorithm (tDNA)²³ adapted to Venezuela²⁴, which includes a stepwise an approach to detect subjects at risk using locally validated tool (LA-FIDNRISC)²⁵, and a protocolized intervention to provide medical nutrition therapy that includes structured low-calorie meal plan, diabetes-specific meal replacements, as well as, start or increase physical activities, get enough sleep, and tobacco cessation. (Figure 2 – Supplement). Our work also includes cultural adaption of the DPP content to the Venezuelan population (e.g. change the names of foods, units of measure, incorporate local healthy foods, warning for unhealthy traditions) and the implementation of two pilot studies (More details below).

To prevent T2D effectively, LSI programs need to induce weight loss. In the DPP, weight reduction was the main predictor of a lower incidence of T2D, each kilogram lost was related with 16% lower incidence²⁶. Total diet replacement (TDR) with low-energy liquid-diet or solid diet (825–853 kcal/day) is an effective strategy to reduce weight²⁷. In the PREVIEW study, 2224 participants with prediabetes and obesity received a low energy

diet during 8-week and presented a mean weight loss of $10.7 \pm 0.4 \text{ kg}^{28}$, and 83.5% achieved the target of $\geq 8\%$ weight reduction, the three-years expected incidence of T2D was only 4%, independent on the intervention used post-weight-loss²⁹. However, effectiveness of intervention including initial rapid weight loss is ignored in primary care levels in Venezuela. In order to improve the effectiveness of T2D prevention programs are proposed the following objectives:

- To compare the weight loss achieved of two LSI programs in a community health center of Venezuela: **a)** A hybrid LSI including rapid weight loss with total diet replacement (TDR), then medical nutrition therapy (MNT), and the DPP, VS **b)** only the DPP.
- To evaluate the change of cardiometabolic risk factors between groups.
- To evaluate the implementation process.

Our hypothesis is: after six months of intervention, subjects receiving a hybridized LSI (TDR+MNT+DPP) will double the weight loss of those that only receive DPP (This is based on the pilot study – see below). If this outcome is achieved, it will have an enormous impact in the way that the DPP should be provided in the primary health care systems in developing countries, increasing the effectiveness of weight reduction, and in consequence, improving cardiovascular health.

Approach

Design: A pragmatic mix trial was designed with two groups a) subjects receiving a hybridized LSI (TDR-MNT-DPP) and b) only DPP.

Population: In Venezuela, there are many community health care centers (CHCs) attended by general physicians. Many of these are “communal houses”, with different activities like dancing, aerobics, yoga, karate, etc. The CHC selected is in Mérida city, at the Andes region, with around 508.988 inhabitants, in 2018. The population is organized in "Communal Councils", representing a location or small sector, two or more create the "Commonwealth", representing neighborhoods or sectors. The CHC selected is in a commonwealth, mid-class urban area, easily accessible for the inhabitants. Community leaders are highly motivated to promote this kind of activities in their neighborhood.

Inclusion Criteria: Adults with 20 years or older, no personal history of T2D, $\text{BMI} \geq 25 \text{ kg/m}^2$, and high risk for T2D (see below) will be included.

Exclusion criteria: Self-report of the following conditions:

- Chronic ischemic heart disease: acute myocardial infarction, stable angina, unstable angina.
- Stroke.
- Use of anticoagulants
- Severe renal failure
- Heart failure.
- Cannot do moderate-intensity physical activity
- Cannot attend most sessions
- Pregnancy or plans of having during the next sixth months
- Cancer or chemotherapy.
- Use of medications that affect weight (e.g. levothyroxine, pregabalin, orlistat)

During the physical examination by the general practitioner:

- Peripheral obstructive arteriopathy.
- Osteoarthritis of knees, ankles or hips.
- Body mass index (BMI) $\geq 40 \text{ kg/m}^2$

- Systolic blood pressure \geq 180 mmHg or diastolic blood pressure \geq 110 mmHg.

At the end of the pilot study, emigration was the most important cause of dropout. Subjects with plans of migration in the following months during the study will be excluded. To avoid contamination risk, if a family member is selected, only one member per family will be included.

Sampling: Community members will be invited to a medical screening at the CHC. Those with high risk will be identified using the Latin America Finish Diabetes Risk Score (LA-FINRISC). The LA-FINRISC is a non-invasive tool that includes age, body mass index (BMI), waist circumference, physical activity, daily consumption of fruits and vegetables, history of hyperglycemia, history of antihypertensive drug treatment, and family history of diabetes, assigning a score ranging from 0 to 26 points. In Venezuelan adults, 9 points are the best score (sensitivity 71.4% + specificity 65.4%) to detect subjects with impaired glucose tolerance²⁵. Those with an LA-FINRISC \geq 10 points and having the inclusion criteria will be invited to laboratory test and medical evaluation and those with laboratory criteria will be invited to participate.

Sample Size: The formula to compare two mean was used. Based on preliminary results of our pilot study, the aim was to detect a two-fold reduction of weight loss in the intensive group (mean = 5.0 kg, standard deviation = 4.9) compared with only DPP (mean = 2.4 kg, standard deviation = 1.9). Using a Beta error of 0.2 and an Alpha error of 0.01, the sample size required for each group is 50, and assuming a 20% of loss to follow up (based on the pilot study), and a 30% additional to ensure representativeness of the sample and power, the sample size will be incremented to **78** participants in each group, total sample size of 156 participants.

Randomization: Eligible participants will be randomly assigned to hybridized LSI or standard care with 1:1 allocation.

Implementation:

Diabetes Prevention Program: The DPP Group Lifestyle Balance (GLB) core curriculum content modified from the original DPP is available online, in both English and Spanish. Despite the intent of facilitating T2D care for the U.S. Hispanic population, the advantage of the Spanish language version, and the robust and general recommendations in which the DPP GLB program is based, this effort was not a true transculturalization process. Important differences among various ethnocultural co-populations and environments were not addressed. For example, in Venezuela, there are unique culinary customs: units of measure during food preparation, types of whole foods in their natural form, and recipes with foods that are not easily available. In addition, recommendations of physical activities must be feasible for a certain population based on religious customs, social norms, the built environment, climate and terrain, and socioeconomic constraints; even, there are food patterns and behaviors regionally different in the same country²³.

The tDNA process was implemented in the following steps to undertake the transcultural adaptation of the DPP content: 1) *Identification target population:* adult's population in Venezuela. 2) *Identification of the topic or research/clinical question:* One out three adults in Venezuela has prediabetes. Evidence-based solutions are required to reduce diabetes burden in Venezuela. 3) *Team of experts in the source (DPP) and target population (Venezuelan culture):* A group of Venezuelan experts composed by four diabetologists, one primary care physician, and two community members trained and certificate by this team to provide T2D prevention programs implemented the adaptive content of the DPP GLB program. 4) *Identification and resolution of cultural nodes using a framework:* The DPP content was organized with the Ecological Validity Model (EVM)³⁰. Using an interactive process each discrepancy between the content and cultural or local costumes were identified and modified in base to the EVM framework (e.g. recipes were adapted to the current socio-economic moment of the country). Finally, T2D prevention curriculum content was culturally adapted to Venezuelan adults avoiding any incongruence with the original version. Healthy options, goal settings, and problem-solving were consistent attributes of the culturally adapted program. Details of this transcultural adaptation will be published soon. This content was used in the pilot study.

Low-Energy Liquid-Diet (LELD): LELD, structured food reintroduction, and then a weight-loss maintenance program have demonstrated being a feasible and acceptable strategy to lose and maintain weight during 12 months²⁷. A “home-made” milk- and fruit-juice-based diet (811 kcal/day, 64 g protein, 132 g carbohydrate, 6 g fat) will be recommended. Recipes and preparation techniques were transculturally adapted to the population using local available low-cost foods in Venezuela. A pilot study assessing acceptability, appropriateness, and feasibility of this LELD strategy in 14 Venezuelan adults with obesity is ongoing.

Implementation Process – The Pilot Studies

A major concern was the feasibility to implement an LSI program in the current environment of Venezuela. A pilot study implementing the DPP-tDNA was done in 26 adults in the CHC. Preliminary results are summarized in Table 1. Results are presented using the implementation process framework³¹.

	n	%
Feasibility		
Screening	67	100.0
Invited to Evaluation (Meet the inclusion criteria)	47	70.1
Assisted to the Evaluation (% of those invited)	36	76.6
Started the Program	26	72.2
Assisted to only 1 session	4	15.4
Drop out (total)	7	26.9
Completed 3 months of intervention (10 sessions)	19	73.1
Fidelity		
Attendance to all the sessions	5	19.2
Attended ≥ 50% sessions	18	94.7
Average of Attendance	6.6	72.1
Acceptability (Likert scale from 1 to 5 points)	4.6	92.0
Appropriateness (Likert scale from 1 to 5 points)	4.6	92.0
Effectiveness		
	n	% Goal†
Mean of weight loss (Kilograms)	2.45	88.2
Subjects that reached the weight goal of the third month	6	31.6

*The pilot study is currently ongoing; these are the results of three months of intervention (50%) with 10 sessions provided. †Goal= to lose 7% of basal weight at the six months, corresponding to 3.5% in the third month.

More details of the implementation process results are in the Supplements (Table 2). Reasons of dropout were: emigration 3 (42.9%), family problems 2 (28.6%), financial problems 1 (14.3%), did not answer 1 (14.3%). Although this pilot study was implemented in the context of a complex humanitarian emergency in Venezuela, with a severe failure of basic services including extensive and repetitive blackouts, scare of gas and gasoline, and the highest inflation rate in the world³², without a budget to provide proper tools to the participants and implementers, the intervention is feasible with a 26.9% of dropout, which is expected in community base scenarios, and with high average of attendance (72.1% - Fidelity). Participants considered the intervention acceptable and appropriate. The mean of weight loss was 2.45 kg in three months and 31.6% had reached the third-month goal.

A second concern was to assess the acceptance of a LELD intervention in Venezuelans. A pilot study to assess its implementation was undertaken in adults with increased weight. A nutritionist provided weekly group sessions recommending “Home-Made” LEDL replacing usual foods during a month, reintroduction diet for 1 week, and then four weekly educative sessions of maintenance weight program. 14 participants assisted to the

first session and nine started the program. In four weeks of intervention, the average weight reduction was 3.23 kg. Using a Likert scale, participants implementing the program (n=9) reported: frequency of secondary symptoms (dizziness, gastrointestinal disorders, headache, hunger, etc.) 0.8/3 points (never = 0 and very frequent = 3); severity of secondary symptoms: 0.5/3 points (mild = 0 and severe = 3); acceptability (satisfaction): 4.9/5 (totally disagree = 1 and totally agree = 5); appropriateness = 5/5 (totally disagree = 1 and totally agree = 5). In summary, the participants reported the intervention acceptable, appropriate, effective, and with a low frequency and intensity of secondary symptoms.

Effectiveness – Intervention. The Flowchart is presented in Supplements (Figure 3).

Duration: 6 months. The DPP has two phases, weight reduction to reach 7% of weight loss during the first six months, and weight maintenance during the next six months. This project aims to evaluate a new strategy to improve the effectiveness of weight reduction in the initial semester.

All participants will be attended by a physician and will receive current guideline recommendations to improve their cardiometabolic health. Healthy lifestyle recommendations including healthy diet, increase physical activity until reach 150 minutes weeks, and weight reduction will be recommended. These encounters will be repeated at the third and sixth months.

Standard Care: a trained peer-led (Coach) will provide a group-based DPP-GLB program in 16-sessions along 6-months. DPP has two primary goals: achieving at least 7% weight loss and engaging in 150 minutes per week of moderate physical activity. Participants will be introduced to self-monitoring of weight and management of the amount and frequency of food consumption, with an emphasis on the reduction of calories coming from fats.

Lifestyle intervention group: Participants in the hybridized LSI group will receive:

- a) The nutritionist will provide a total diet replacement (TDR) with Low-Energy Liquid-Diet (LELD - 811 kcal/day, 64 g protein, 132 g carbohydrate, 6 g fat) and the food reintroduction for two months (Phase 1).
- b) The nutritionist will provide Medical Nutritional Therapy (MNT) using the tDNA Toolkit adapted for Venezuela (Phase 2a).
- c) The coach will provide a group-based DPP-GLB version in weekly encounters during 4-months (Phase 2b) (Similar than standard care)

This hybridized LSI has similar goals than the standard care group: achieving at least 7% weight loss and engaging in 150 minutes per week of moderate physical activity.

In phase 1, nutritionist in group sessions will recommend to participants to lose at least 7% of their weight using LELED for two months. LELED was related in the pilot study with a mean of weekly average weight loss of 0.8 kg. Participants will return after a week, and then bi-weekly encounters until complete food reintroduction. A “Home-Made” LEDL will replace usual foods, vitamin supplements will be recommended to participants during this phase. If during the year of intervention, the participant relapse (weight regain > 2 kg), TDR to replace one or two main-meal per day for 4 weeks will be recommended.

In phase 2 nutritionist will recommend weight maintenance or weight reduction strategies. In phase 2a nutritionist individually will recommend to participants medical nutrition therapy and healthy lifestyle recommendations using the Venezuelan’s tDNA-Toolkit. Phases 2a and 2b will begin simultaneously. In phase 2b, the coach will provide group-based DPP-GLB program in 16-sessions along 4-months. Total intervention time planned include phases 1 and 2 is six months.

Training Peers: Coach can deliver educative programs in an acceptable way to their peers³³ and with similar effectiveness than health professionals^{34,35}. The coach was already selected and trained using a face-to-face

approach during three-days, improving their knowledge on goal setting, action plans, problem-solving, and communications skills. During the intervention process, peers will be supervised and supported.

Side Effects and Weight Regain with Rapid Weight Loss: Beliefs that more intensive interventions and rapid weight loss lead to greater weight regain are not supported by evidence from controlled trials²⁷. In a feasibility study in primary care, 97 participants (mean BMI of 48 kg/m²) were recommended to receive TDR with LELD during 12 weeks, then food reintroduction and weight maintenance plan³⁶. 64% completed the LELD stage with a mean of weight loss of 16.9 ± 6.0 kg. At 12 months, 75% (68/91) assisted to the evaluation and the mean weight loss was 12.4 ± 11.4 kg. In the qualitative analysis some experience transient constipation and dizziness³⁶. In the DiRECT study (Remission of T2D study) was used the LELD during three months, at the year of one year intervention, nine serious adverse events were reported by seven (4%) of 157 participants in the intervention group and two were reported by two (1%) participants in the control group, these included gastrointestinal disorders, dizziness, and abdominal pain³⁷. Those in the intervention group lost 14.5 kg during the TDR phase and then regained 1.0 kg during the food reintroduction phase and 1.9 kg during the maintenance phase³⁷.

Variables Evaluated: The list of variables is summarized in Supplements (Table 3).

Data analysis plan:

Aims comparing effectiveness: I will be done using an intention-to-treat analysis. To evaluate the distribution of values at baseline and after follow-up, Student t-test will be used to compare weight at baseline and at the end of the intervention, as well as, other continues variables (blood pressure, lipid profile, blood glucose, physical activity level, etc.). Chi-square test will be applied to assess the different proportion of subjects that reached their weight goal. To assess the implementation process will be applied the Implementation Outcomes Framework, this was partially reported in this project (Table 1), additionally, it will be evaluated the cost of the intervention. Implementation outcomes will be presented as proportions, means, and qualitative comments.

Research team and their role:

Two Lown Scholars, PI, and mentor designed the study, are going to supervise the implementation, do the analysis, and write the paper. An investigator from Icahn School of Medicine at Mount Sinai, New York, NY, USA, four co-investigators from the EVESCAM Research team, collaborated with the design and will collaborate with supervision of implementation, data analysis, and critical review. Implementers will coordinate intervention. The organizational structure includes: (a) Collaborative coordinating institution: Venezuelan Society of Internal Medicine (SVMI), Caracas, Venezuela; (b) Cardiometabolic Unit, Barquisimeto, Venezuela, where it is located laboratory (c) Field center: the Community health care center (d) Investigators (e) International consultants; (f) Local coordinators (n=2); (g) Nutritionist and research assistant (n=2); (h) Certified Coach (n=1). The budget will be administrated by the Foundation for Clinical, Public Health, and Epidemiological Research of Venezuela (FISPEVEN). See support letters

Timeline:

Months	1 - 3	4 - 9	10 – 12
Screening and Medical Evaluation	X		
Intervention		X	
Data analysis and draft writing			X

Challenges and Alternative Response

According to the observed in the pilot studies, there are two major challenges: a) *high dropout and lower fidelity*: a 20% of dropout is expected, however, implementers will be trained to be in continuous contact with the participants and maintain them highly motivated. Workshops of cooking and group physical activities are two

examples of activities that increased motivation and attendance rates. B) *Not compliance with the TDR*: In the pilot study, TDR showed being an effective way to lose weight, however, some participants didn't accept the TDR, others changed the components frequently, and some only replaced one or two main plates, to avoid these threats, well-designed recipes with lower cost available foods showed increase compliance, additionally, in the first session it will include a workshop of how to prepare different milkshakes, and how to improve its taste, and increase volume without increasing calories to avoid hunger, a large list of different milkshakes will be provided.

Ethics:

This project will be registered in ClinicalTrials.gov. This study protocol was designed in compliance with the Helsinki declaration. The protocol and informed consent forms used in this project will be reviewed and approved by an ethics committee in Venezuela before its implementation. A researcher will read all the informed consent to the participant and will explain the benefits and risk of participation in the study answering all his/her questions, this includes: rationale of the study, identification of subjects at risk, random assignment, responsibilities, duration, potential health benefits, data management (with special emphasis in their confidentiality), and willingness to participate, including that his/her participation it can last as long as the participant want (for more detail see Informed Consent). Then, if the participant decides to participate will sign the informed consent. This will take place in the primary health care center where the intervention will be done, after the campaign of screening of risk factors in the community.

Management of Secondary Effects:

All the participants will be attended by a specialist in Internal Medicine three times throughout the study. A general practitioner will attend with the nutritionist to all the sessions of the implementation of the liquid diet, this represents that this will be under weekly medical surveillance during the most sensitive part of the process. Then, this physician will attend at least one per month to each session of the participants. If the patient presents an acute medical problem will be able to call the general physician of the team to receive medical attention, and this will be provided in the community health care center of the community, in case of more specialized advice, the general practitioner can request help to the specialist of internal medicine to attend the patient. If it is observed a secondary effect consequence to the intervention the nutritionist or the coach will modify the intervention according to the recommendations provided by the doctors to avoid related complications. All this medical attention potentially related to the participation of the study will be provided for free to the participants.

References

1. Global, regional, and national disability-adjusted life-years (DALYs) for 359 diseases and injuries and healthy life expectancy (HALE) for 195 countries and territories, 1990-2017: a systematic analysis for the Global Burden of Disease Study 2017. *Lancet* (London, England) 2018;392:1859-922.
2. Institute for Health Metrics and Evaluation (IHME). Venezuela Profile 2007 - 2017. Accessed on May, 2019. Available online: <https://vizhub.healthdata.org/gbd-compare/>.

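### Outcomes may be correlated within the session groups that deliver treatment in both arms, and the sample size and named between-arm tests make no allowance for it

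*Protocol*

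**What the plan says.** The first objective is a between-arm one: "To compare the weight loss achieved of two LSI programs in a community health center of Venezuela". Under Randomization, "Eligible participants will be randomly assigned to hybridized LSI or standard care with 1:1 allocation". The unit of allocation is the person, and "only one member per family will be included".

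Delivery is largely by group. Under Standard Care, "a trained peer-led (Coach) will provide a group-based DPP-GLB program in 16-sessions along 6-months". In the hybrid arm the nutritionist runs phase 1 in group sessions, and the coach runs phase 2b as a group-based course of 16 sessions over four months. The individual parts are phase 2a and the physician encounters that all participants have. The research team includes one certified coach.

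Under Sample Size, "The formula to compare two mean was used". The planning inputs are "Using a Beta error of 0.2 and an Alpha error of 0.01", with losses of 5.0 kg (SD 4.9) and 2.4 kg (SD 1.9). This gives 50 per arm, which is raised for 20% loss to follow-up and for "a 30% additional to ensure representativeness of the sample and power", to 78 per arm.

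The Data analysis plan names a Student t-test for weight and other continuous variables and a chi-square test for the proportion reaching the weight goal. It gives no test level. The flowchart and variable list are in Supplements that are not shown.

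**The concern.** People who share a session group share its atmosphere, its attendance habits and any disruption to it. The section Challenges and Alternative Response credits group activities with raising motivation and attendance. That is a plausible route to correlated outcomes, though not a measure of it.

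Under positive correlation, 62 people in a few groups carry less information than 62 independent people. A plain t-test or chi-square test between arms then uses too small a standard error. It rejects a true null hypothesis more often than its nominal level, and a confidence interval built on the same standard error is too narrow. The primary aim and the 7% goal are both exposed.

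**Working it through.** **Reproducing the plan's figure.** From Sample Size: difference 5.0 − 2.4 = 2.6 kg, and sum of variances 4.9² + 1.9² = 24.01 + 3.61 = 27.62. For two-sided alpha 0.01 and 80% power, n = (2.576 + 0.842)² × 27.62 / 2.6² = 47.7 per arm, close to the stated 50. Then 50 × 1.2 × 1.3 = 78. This is an independent-observations calculation with a design effect of 1.

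**Inputs for the check.** Evaluable per arm: 78 × 0.8 = 62.4, taken as 62. Assumed, because the text shown does not give them: k = 6 or 3 groups per arm, and ICC 0.01 to 0.05.

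**Formulas.**
- Group size m = 62/k; design effect DE = 1 + (m − 1) × ICC.
- True level of the plain test = 2 × [1 − Φ(z/√DE)], with z = 2.576 (nominal 1%) or 1.960 (nominal 5%).
- Understatement of the standard error = 1 − 1/√DE.
- Large-sample power at 0.01 = Φ(2.6/SE − 2.576), with SE = √(27.62 × DE/62).
- Group-mean t-test: noncentral t with the same SE and Welch-Satterthwaite df = (k − 1) × 27.62² / (24.01² + 3.61²) = 1.294 × (k − 1).

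**Worked case**, six groups and ICC 0.05: m = 10.33; DE = 1 + 9.33 × 0.05 = 1.47; √DE = 1.211; 2.576/1.211 = 2.127; true level 3.3%.

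| ICC 0.01 to 0.05 | Six groups per arm | Three groups per arm |
|---|---|---|
| Design effect | 1.09 to 1.47 | 1.20 to 1.98 |
| Standard error understated by | 4% to 17% | 9% to 29% |
| True level at nominal 1% | 1.4% to 3.3% | 1.9% to 6.7% |
| True level at nominal 5% | 6.1% to 10.6% | 7.3% to 16.4% |
| Coverage of a 95% CI | 93.9% to 89.4% | 92.7% to 83.6% |
| Large-sample power at 0.01 (91% at ICC 0) | 88% to 74% | 84% to 58% |
| Group-mean test: df | 6.5 | 2.6 |
| Group-mean test: power at 0.01 | 58% to 44% | 20% to 12% |
| Group-mean test: power at 0.05 | 88% to 78% | 60% to 43% |

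Simulation of the plain t-test (40,000 trials per case) agrees: 1.5% to 3.6% with six groups and 1.9% to 7.0% with three at nominal 1%, against 1.1% at ICC 0. For the chi-square test on the goal, with an assumed goal rate of 30% to 50% in both arms, the simulated levels at nominal 1% are 1.2% to 3.6% and 1.7% to 6.9%.

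**The 30% reserve.** With DE = 1, 2.6/SE = 3.895. Power stays at 80% while DE ≤ (3.895/3.418)² = 1.30. That corresponds to ICC 0.30/9.33 = 0.032 with six groups, or 0.30/19.67 = 0.015 with three. The reserve adds people. It does not change how the standard error is computed, so the test level is not protected.

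**Not every correction works for the goal.** An uncorrected cluster-robust z-test (assumed goal rate 40%, 40,000 simulated trials per case) rejects about 4% with six groups and about 10% with three at nominal 1%, even at ICC 0. A group-level t-test on proportions holds about 1%.

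**The case against.** The strongest reply is that the size is wholly assumed. With six groups and ICC 0.01, the level moves only from 1.0% to 1.4%. At the planning level of 0.01 it stays below 5% throughout the six-group range. That stands. It is an argument for stating a range, though, not for a test that in effect takes the ICC as exactly zero.

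Second, the analysis plan's t-test sentence can be read as baseline versus end, or as comparing weight itself and not change. If follow-up weight is compared, with an assumed SD of 10 to 15 kg, the worst case above (three groups, ICC 0.05) shrinks to 1.2% to 1.6% at nominal 1%. The ambiguity is real, but the first objective and the sample size are both framed in weight loss.

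Third, a statistical analysis plan that is not shown could add a cluster adjustment. It could override the tests, but it would not change the basis on which 156 was set. Session group may also be hard to recover if it is not recorded at delivery.

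Fourth, correcting costs power. At six groups and ICC 0.01, a group-mean test gives up about 30 points (88% to 58%) to correct the level by 0.4 points. That is a fair objection to a mechanical correction and is why the fix has a fallback.

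A reader might infer several stronger things that the protocol does not support:
- *Every between-arm comparison is affected.* Baseline values precede treatment, so group delivery cannot correlate them.
- *The single coach biases the comparison.* One coach serves the trial, so a common coach effect does not separate the arms. The unit at issue is the session group.
- *Treatment is entirely grouped.* Phase 2a and the physician visits are individual, and the one-per-family rule removes another source of correlation.

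**Conclusion.** The point holds conditionally. Group delivery in both arms and independence-based planning and tests are in the text. The direction of the error follows for any positive within-group correlation of post-treatment outcomes. It concerns the between-arm comparisons of follow-up weight change and of the 7% goal.

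The size cannot be fixed from the protocol. It could be slight or, with few large groups and ICC near 0.05, several times the nominal 1%. It would be wrong to conclude that the trial's error rate is known to be inflated, or that 156 participants are too few. At the planned level, 80% large-sample power survives modest clustering. The change is worth making because recording the group is cheap and may be hard to do afterwards. Confidence in its practical importance is moderate.

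**What to change.** 1. Record each participant's session group. In the hybrid arm, record phase 1 and phase 2b groups separately if they differ, and state in advance which is modelled. State the planned number and size of groups if the Supplements do not.
2. For the between-arm comparison, account for session group with a small-sample correction for **both** outcomes. For weight change, use a mixed model with arm-specific variances and Satterthwaite or Kenward-Roger degrees of freedom. For the 7% goal, use a group-level t-test on proportions or a small-sample-corrected robust method, not an uncorrected robust z-test.
3. If there are too few groups to estimate the group variance, for example one to three per arm, say so, keep the simple analysis, and report the between-arm confidence interval over a pre-stated range of ICCs.
4. Restate the power of 156 participants over that range, for the analysis and test level actually to be used.

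Cost: one or two recorded variables, revised wording, lower stated power and wider intervals. The group-mean powers in the table are conservative; a mixed model may have more degrees of freedom when the estimated group variance is near zero. No extra participants or staff are needed if the lower power is accepted. More, smaller groups recover some power: with eight per arm, the group-mean test has 69% to 57% at 0.01. That means 2 × 8 × 16 = 256 DPP sessions from one coach, against 2 × 6 × 16 = 192 for six and 2 × 3 × 16 = 96 for three.
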